Despite the intense neuroscientific and translational interest, these lines of research do not converge. At present, there is little understanding how any ER-based therapies influence ER brain function. The goal of this pilot study is to collect preliminary data that will allow us to formulate theories about ER-related brain function change during intervention-like training that will be tested in larger, externally-funded grant proposals submitted to the National Institutes of Health. We are not especially interested in any existing specific, manualized therapeutic technique. Existing ER-based psychotherapies typically incorporate a variety of related interventions, not all of which focus on the ER component itself. Instead, we focus on the “building blocks” of such therapies, i.e., the ER interventions themselves and their effect on negative emotional reactions. Here, we ask a specific question – How does ER-elicited brain function change with repeated sessions of guided practice of various ER techniques? In other words, does increasing familiarity or mastery of ER skills through practice change brain function, and how? There are logical hypotheses about the likely nature of brain function changes that can be gleaned from prior neuroimaging research. For instance, if prefrontal cortex activation is important to ER, perhaps practice simply increases such activation. However, our pilot work for the current NIMH R01 suggests instead that ER practice might work by enhancing the functional integration among key frontolimbic regions. Complicating such hypotheses is the recognition that different ER tactics engage many distinct brain regions depending on which approach is employed. So a person’s individual brain function differences prior to ER training might be a potent determinant for what sorts of neural changes result from repeated practice. Because all these issues must be evaluated through the lens of a preliminary study before any coherent theoretical model can be formulated, we propose a pilot study here. Not only will this provide empirical data upon which to base future research, conducting such a pilot will showcase any methodological hurdles or challenges that need to be overcome in order to successfully conduct a larger-scale study.

APPROACH

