N=40 adults (ages 18-50, approximately equal numbers of males and females) who are pre-screened to have mild-to-moderate levels of depression or who will serve as non-depressed/anxious controls will be recruited from community resources. Inclusion criteria are described in detail in the Human Subjects section. In brief, we will operationalize inclusion for the depressed group as any participant who scores >1.5 SD from normative levels on the Beck-Depression Inventory-II. Elevated trait anxiety on the Spielberger’s State/Trait Anxiety Inventory (STAI) will not disqualify inclusion (as depression and anxiety commonly co-occur). Any depression

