symptoms will not have to reach diagnosable levels of Major Depressive Disorder to qualify for the study. The non-clinical control group will have minimal symptoms on the BDI-II and State/Trait scales. Participants in each of these study groups then will be randomized into two conditions ($n=10$), each of which will receive 2 assessment/MRI appointments along with 6 sessions of guided practice/training in either 1) Re-interpretation or 2) Mindfulness ER techniques. If randomized into the CBT-based regulation training, subjects will be trained to use a cognitive strategy that instructs them to reappraise situations in positive or less negative ways. If randomized into the MBT-based regulation training, subjects will be trained to use a mindfulness strategy that instructs them to notice and accept their feelings without judgment or intent to act upon them. In both conditions subjects will be shown pictures of negative-affective stimuli and asked to use the strategy over and over again. These appointments will take place 'virtually' using a laptop computer that is set up at the participants house and is controlled remotely by Olin NRC staff. The training sessions will then be monitored by the research assistant via Skype, so that the participant can be given instructions and supervised while completing each session. "Training" in this context is conceptualized as the cumulative amount of practice, with the expectation that greater practice leads to greater mastery. Immediately after the first and sixth practice sessions, participants also will undergo fMRI so that brain function relative to that stage of practice can be assessed. In brief, training will be guided-practice sessions where examples of ER tactics are explained, modeled, then practiced with interactive discussion and feedback. To clarify, the primary outcomes for this pilot study will be fMRI-assessed brain function data, examined either to detect any changes in activation amplitude ("level of activity") in *a priori* ER-linked brain regions-of-interest (ROIs) (Table 1) or changes in the degree of functional connectivity among them. Secondary outcomes will be the BDI-II and STAI. Because we have a well-established infrastructure that includes many other datatypes useful for emotion-related neuroscience, we also will collect a variety of other individual-level data for exploratory analyses. By design, we propose to cast a wide net to collect information on the most relevant factors suggested by prior research to be explored. All data collection methods are described next, followed by a brief data analysis plan.

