Accurate ROI identification will utilize ICA, in part to reduce the data into a small handful of datapoints. ICA was developed to solve the "cocktail party" problem in which many people are speaking at once ¹¹¹. ICA separates mixed signals into individual sources (e.g., "voices") based on unique temporal characteristics of each signal. When applied to fMRI data, spatial ICA assumes there is a set of non-systematically overlapping (temporally independent) brain regions (or small networks) with unique time courses. When ICA fits a high model order to the data (i.e., asking for >80-130 components) (e.g., ¹¹²⁻¹¹⁵), components typically depict activity in just 1 or 2 brain regions (e.g., Fig 6), or isolate anatomical sub-regions (e.g., basolateral vs. centromedial nuclei). Localization is quantitatively facilitated by correlation with *a priori* templates (e.g., MNI or cytoarchitectonic ¹¹⁶ atlases). Our whole brain group fMRI ICA methods ¹¹⁷ include a reconstruction step that projects the group-derived ICA solution back onto each participant in a way that preserves individual variability in each spatial map and timecourse for further analysis. We have used these ICA methods in many dozens of previous fMRI studies (e.g., ^{115, 118-130}), and successfully applied ICA individual timecourses to DCM and other effective connectivity applications ^{119, 121}. Alternatively, semi-blind ICA methods we developed ¹³¹ balance atlas-based ROI selection (e.g., from ER meta-analysis ^{5, 23}) with subject-specific data-driven influences. Finally, ICA is a widely-appreciated "denoising" technique, in fact originally designed to isolate meaningful signals from background noise. Not only does it isolate signal corresponding to head motion artifacts from ROI activity, metrics can confirm ROI signals are free from motion-related noise (e.g., comparison of low-frequency / high-frequency BOLD signal oscillations ¹¹⁵).

Analysis Plan The core analyses will employ a 4 (ER group) × 2 (training timepoint) mixed-effects ANOVA to V3 Rev 6/5/2019

[figure not shown]

Fig. 6: ICA-localization to (A) bilateral dlPFC and (B) right BL amygdala ($t=15$ min threshold) from pilot data.

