test a general hypothesis that brain function or functional connectivity will change for the ROIs being studied. Because there will be 8 ROIs, we will consider results when using a Bonferroni-corrected α of .00625. However, because this is a pilot study, that correction will not be strictly imposed; rather, its use primarily will help us to decide whether any preliminary data might be publication-capable. *Supplemental Analyses:* Because this is a pilot study, we plan to assess the relationship of fMRI-measured ER brain function change throughout training to numerous other factors. Foremost, we need to evaluate whether non-neural measures of emotional function are altered by the ER training. We will use repeated-measures ANOVA to assess whether or not self-ratings of emotional intensity, SCR, pupil size/fixation time to emotional stimuli change across the fMRI sessions. We also will assess if POMS-2, BDI-II or STAI scores collected at baseline and in the final session differ, as these are clinically-relevant indicators of change that is independent of the ER training itself. Typically in this sort of fMRI experimentation, the degree of change in these measures also is correlated with the degree of change in any brain regions found in the primary analysis to bolster the case of the potential clinical relevance of the findings in *post hoc* analyses.

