Power Analysis Because this is a pilot study, one of its goals is to allow us to assess the size of any effects. Therefore, our sample size must be adequate so that the effort of data collection is worthwhile. A hypothetical power analysis for a repeated-measures ANOVA for just one of the 3 experimental conditions can control Type II error ($1-\beta=.80$) effectively to detect "large" effect size differences ($d=0.94$) across the 2 fMRI sessions in any single brain region (including Greenhouse-Geiser corrections). If that hypothetical model is expanded to include all three ER training groups simultaneously as planned, the total $N=40$ sample can detect large group difference effect sizes. Changes in brain activity over time common to all groups can be detected if their effect size is as small as $d=0.48$ (or "medium"). Finally, the planned analyses can detect $d=0.56$ effect sizes for the interaction of group \times training timepoint. This makes us confident that the proposed sample size will be adequate for both identifying scientifically-notable effects in the data and allow us to empirically-support their magnitude for future study design planning.

HUMAN SUBJECTS

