Human Subjects Involvement and Characteristics All potential participants will undergo initial telephone screening to ensure they meet general inclusion/exclusion criteria. Qualified participants will then meet with study staff for informed consent. Following consent, they will undergo psychiatric interview and complete a battery of questionnaires to ensure none of the study exclusion criteria are met. At this point, participants will be randomized to one of the two ER training conditions (Reinterpretation or Mindfulness). The protocol requires 6 visits over three consecutive weeks at a time that is convenient for participants, and that they agree they can accommodate. We will attempt to structure an ideal schedule of appointments each week that follows a Mon/Wed, Tue/Thu, or Wed/Fri format. At each appointment, participants will undergo guided training in a specific ER tactic. Also, at the first and last MRI appointments, participants will complete a 60-minute fMRI

session. Prior to fMRI, participants will be tested for the presence of drugs and pregnancy (if female) through urinalysis.

Inclusion/Exclusion Criteria Inclusion: Ages 18-50, right-handed, a high-school level of education (11th grade attainment for 18 year-olds is acceptable if they haven't completed their final year yet), and \geq 8th grade English reading level to complete self-report evaluations (most are only available in English). Exclusion: Medical history that will exclude any potential participant includes head injury sufficient to have caused >30 minutes lost consciousness; past or current CNS disease (e.g., MS, epilepsy, tumor, etc.) or brain lesion identified by MR (structural MR scans will be reviewed by a radiologist for the presence of clinical neuropathology that may affect cognitive task performance); hypertension or juvenile-onset diabetes (current treatment with antihypertensives or insulin); current pregnancy (menstruating females will be tested). Psychiatric exclusion criteria include DSM-IV Axis I lifetime history of Bipolar disorder, PTSD, OCD, psychotic disorder, Tourette's disorder, or any Pervasive Developmental Disorder (e.g., Autistic disorder, PDD NOS, etc.); current DSM-IV substance dependence, ADHD, Conduct Disorder. Any participant who currently takes psychotropic medications will be excluded, even if psychiatric diagnostic criteria are not met.

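### The four-level ER group factor appears to merge non-randomised symptom group with randomised training, and the plan names no test that isolates the randomised comparison of the two strategies

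*Combined protocol and SAP*

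**What the plan says.** The Approach section recruits 40 adults "who are pre-screened to have mild-to-moderate levels of depression or who will serve as non-depressed/anxious controls". It continues: "Participants in each of these study groups then will be randomized into two conditions", with 10 per condition. Human Subjects Involvement and Characteristics confirms two arms: "participants will be randomized to one of the two ER training conditions (Reinterpretation or Mindfulness").

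The Analysis Plan gives the core model: "The core analyses will employ a 4 (ER group) × 2 (training timepoint) mixed-effects ANOVA". Its stated purpose is to "test a general hypothesis that brain function or functional connectivity will change for the ROIs being studied". The four levels are not listed. The Bonferroni reference of .00625 for 8 ROIs is given but is expressly not binding.

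The Power Analysis counts differently. It starts from one of three conditions and goes on: "If that hypothetical model is expanded to include all three ER training groups simultaneously as planned". It then says that "the planned analyses can detect $d=0.56$ effect sizes for the interaction of group" × training timepoint. It does not state the alpha, the between-scan correlation or the scale of d.

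**The concern.** Only one of the two factors inside the four-level group is randomised. Symptom group is set by screening scores. The group × time term in a 4 × 2 model asks whether any of the four cells changes differently from the others. It does not say whether the source is training, symptom group or their combination.

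The plan itself gives reason to expect symptom group to matter. Synthesis and Formulation says that "individual brain function differences prior to ER training might be a potent determinant for what sorts of neural changes result from repeated practice". Such a result would be of interest, but it answers a non-randomised question. The comparison that randomisation protects, reinterpretation against mindfulness, has no named test. The generic mention of comparing group profiles under Conventional fMRI Analyses does not supply one.

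At stake is what the pilot hands on. The Power Analysis wants effect sizes for planning later studies. A 3-df effect that mixes diagnosis with training cannot size a trial comparing strategies.

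**Working it through.** **Inputs.** From the documents: N = 40; two symptom groups; two arms; 10 per cell (2 × 2 × 10 = 40); two scans; interaction effect d = 0.56; target power .80; reference alpha .00625 = .05/8. Assumed because not stated: alpha .05 for the power figures, between-scan correlation ρ = 0.5 (other values shown), and d = 2f.

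**Degrees of freedom.** Group × time: (4 − 1)(2 − 1) = 3. Error: 40 − 4 = 36. The 3 df split into training × time, symptom × time and training × symptom × time, 1 df each.

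**Reproducing the plan's figure.** Noncentrality λ = f²·N·2/(1 − ρ), with f = 0.56/2 = 0.28.
- Four cells, ρ = 0.5: λ = 0.0784 × 80/0.5 = 12.54; F(3,36) power is 81%. The effect detectable with 80% power is d = 0.55.
- Four cells at other correlations: 66% at ρ = 0.3 and 90% at ρ = 0.6.
- Three groups, F(2,37): 87% at ρ = 0.5, and 80% only near ρ = 0.4.

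So d = 0.56 is compatible with the four-cell omnibus under these assumptions, although the surrounding text counts three groups.

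**Scale.** For a difference D in mean change between two halves of the sample, in SDs of the change score, λ = 40·D²/4 = 10·D². Setting 10·D² = 12.54 gives D = 1.12. At ρ = 0.5 the plan's d = 0.56 is therefore a 1.12 SD difference in change. If 0.56 were instead read as SDs of change, λ would be 3.14 and power 41% (1 df) against 26% (omnibus).

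**Attribution and power.** The omnibus rejects equally often whether D comes from symptom group alone or training alone. The 1-df column applies when D is a training difference. When D is a symptom difference only, the training contrast rejects at its nominal level.

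| D (SD of change) | λ | Omnibus, .05 | Training 1 df, .05 | Omnibus, .00625 | Training 1 df, .00625 |
|---|---|---|---|---|---|
| 0.50 | 2.50 | 21% | 34% | 5% | 11% |
| 0.80 | 6.40 | 50% | 69% | 20% | 37% |
| 0.91 | 8.28 | 62% | 80% | 29% | 50% |
| 1.12 | 12.54 | 81% | 93% | 51% | 73% |

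Simulation (40,000 runs) of a symptom-only difference of 1.12 SD gave 81.5% for the omnibus and 5.0% for the training contrast.

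**Where the omnibus does better.** If change is confined to one cell, the between-cell variation splits equally over the three 1-df terms. At total λ = 12.54 the training contrast receives 12.54/3 = 4.18, so its power is 51% against 81% for the omnibus. If the effect is purely symptom × training, the training contrast stays at 5%.

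**The case against.** The strongest reply is that this is a wide-net pilot with a general hypothesis of change. The time main effect addresses that hypothesis, and an omnibus is a reasonable screen when any of several patterns might appear. This stands in part, and the one-cell calculation supports it.

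A reader might infer three stronger charges that the documents do not support.
- *The plan would treat a significant interaction as proof that the strategies differ.* It nowhere says so.
- *The design confounds training with symptom group.* It does not. Training is randomised within each symptom group, so the collected data can separate the factors.
- *The d = 0.56 figure was derived for three groups.* The three-group wording is in an earlier sentence. The d = 0.56 sentence refers to the planned analyses, and four cells reproduce it at alpha .05 and ρ = 0.5.

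Two further limits apply. The omnibus power loss is realised only if the omnibus is the sole or gatekeeping test, which the plan does not state. And the content of the four levels is inferred, though no other reading fits two arms of 10 within each of two symptom groups.

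What remains is that contrasts chosen later are not prespecified. Reading all three 1-df terms at .05 with none named primary gives about a 14% chance of at least one false positive per ROI.

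**Conclusion.** The concern holds as a missing prespecification and a miscounted power statement. A significant group × time term would not by itself show that the strategies differ. How often a symptom-only difference would trigger it depends on an effect the documents do not give: about 21% at 0.5 SD and 81% at 1.12 SD, at alpha .05. For a pure training difference of 0.91 SD of change, the named contrast has 80% power against 62% for the omnibus. The three-group wording contradicts both the two arms and the four cells and needs correcting whatever view is taken of the rest. The tables in SDs of change do not depend on the between-scan correlation; the translation of d = 0.56 does. With a non-binding alpha in a pilot, this is worth fixing because it costs almost nothing. It does not invalidate the study.

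**What to change.** 1. Write the model as training (2) × symptom group (2) × time (2), and list the levels.
2. Prespecify the 1-df training × time contrast as the test of the randomised comparison. Report symptom × time and the three-way term separately as secondary. Keep the 3-df omnibus as exploratory if wanted.
3. Use the same first-level contrast in both arms. The plan allows contrasts against other conditions or rest and does not say which enters the ANOVA. Options are Reappraise minus look-negative and Accept minus look-negative, each in all participants, or trained versus untrained strategy × time. Each arm's own trained strategy minus look-negative should be avoided: it compares different trial types between arms and so mixes instruction with training. Naming one primary contrast keeps one activation test per ROI, which matches the .00625 reference. Two co-primary contrasts would make 16 tests (.05/16 = .003125).
4. Correct the group count in the Power Analysis, and restate the detectable effects with alpha, between-scan correlation and the scale of d. At alpha .05 and ρ = 0.5, training × time is detectable with 80% power at d = 2f = 0.46 (0.91 SD of change); at ρ = 0.3 and 0.6 it is 0.54 and 0.41.
5. Reconcile the scan timing in the Approach (directly after the first and sixth sessions) with the fMRI Assessment Overview (a 5-day window). Do not attribute a bare time effect to training, since there is no untrained arm.

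Cost: wording only, with the same data and software. There are two downsides. More than one 1-df test per ROI means that one must be named primary. The contrast also has less power than the omnibus if change is confined to one cell (51% against 81% at the same noncentrality). Even if all three terms were tested at .05/3, the contrast would hold its own for a pure training difference: 64% against 62% at 0.91 SD.

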Conventional fMRI Analyses FSL FEAT analyses will estimate activation with FMRIB's Improved Linear Model (FILM), using geodesic Gaussian algorithms to estimate autocorrelation and smooth fMRI data. Explanatory Variables (EVs) will use a double-gamma HRF convolution to translate event onsets in conditions of interest into regressors to be fit to the BOLD timeseries. EV contrasts (against other conditions or implicit "rest") will isolate task-induced activation, creating activation maps. The sample data then will be evaluated using FSL's FLAME random-effects models to confirm activation, compare group profiles, etc. Random-effects models for hypothesis-testing will employ PALM ¹¹⁰, a relatively new FSL- and CIFTI-compatible analysis tool. Although we will focus on brain ROIs (Table 1), PALM offers both threshold-free cluster enhancement and corrections for multiple comparisons following permutation-based statistical inference to explore the possible effects of treatment on other brain regions with confidence.

ROI Localization Using Independent Component Analyses (ICA)

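### The single-step Bonferroni benchmark of .00625 for the eight ROIs could be replaced by Holm at no cost in error rate, for a modest gain in power; the Power Analysis should state the level and correlation behind its detectable effects

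*Combined protocol and SAP*

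**What the plan says.** Under Analysis Plan, the core model is a mixed-effects ANOVA with four groups and two timepoints, applied to each of the eight ROIs in Table 1. On multiplicity it says "Because there will be 8 ROIs, we will consider results when using a Bonferroni-corrected" level, which it sets at .00625. The status of that level is qualified at once: "that correction will not be strictly imposed; rather, its use primarily will help us to decide whether any preliminary data might be publication-capable".

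Under Conventional fMRI Analyses, the plan names a permutation tool for its random-effects hypothesis tests: "PALM offers both threshold-free cluster enhancement and corrections for multiple comparisons following permutation-based statistical inference". The stated purpose of that correction is to explore brain regions outside the ROI set, not to handle the eight-ROI family.

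Under Power Analysis, three detectable effects are given at 80% power. The first, for one condition alone, is "effect size differences ($d=0.94$) across the 2 fMRI sessions in any single brain region". The second is for the time effect: "Changes in brain activity over time common to all groups can be detected if their effect size is as small as" d=0.48. The third is d=0.56 for group by timepoint. The section gives no alpha and no between-session correlation. It speaks of three conditions or groups, where the Analysis Plan has four.

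**The concern.** Single-step Bonferroni compares every p-value with .05/8. Holm starts at the same value and relaxes it after each rejection, with the same family-wise guarantee under any dependence among the tests. Bonferroni is valid, but a uniformly better procedure is available at no cost. The choice matters most if several ROIs change together, which the protocol's account of prefrontal control over the amygdala makes plausible.

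The second matter is that the benchmark and the power statement are not tied together. The Power Analysis concludes that the sample is adequate, but a reader cannot tell whether its detectable effects refer to .05 or to the .00625 used to judge results. The pilot is meant to inform the design of larger studies, so the ambiguity would carry forward.

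**Working it through.** **Inputs from the documents.** Eight ROIs, level .00625, N=40, n=10 per cell, four groups by two timepoints, power .80, and d = 0.94, 0.48 and 0.56.

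**Assumptions, because the documents are silent.** f=d/2, no dropout, between-session correlation r=.5 (range shown), and equal correlation of 0 to .7 among ROI change scores.

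**1. The plan's level.** .05/8 = .00625, which reproduces exactly. With independent tests the family-wise error is 1-(1-.00625)^8 = 4.9%. In simulation it is about 4.6-4.8% at ROI correlation .3, 4% at .5 and 3.3% at .7. Bonferroni therefore wastes little unless the ROIs are strongly correlated.

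**2. The plan's detectable effects.** The noncentrality is λ = (d/2)²·2N/(1-r). Error df are 40-4 = 36; numerator df are 1 for time and 3 for group by time.

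- Time, d=0.48, r=.5: λ = 0.24²·80/.5 = 9.22. Power is 84% at .05 (80% detectable d = 0.455) and 56% at .00625 (detectable d = 0.60).
- Group by time, d=0.56, r=.5: λ = 0.28²·80/.5 = 12.54. Power is 81% at .05 and 51% at .00625 (detectable d = 0.71).
- One condition, d=0.94, n=10, r=.5: power is 75% at .05 (detectable d = 1.00) and 36% at .00625.

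So alpha .05 with r=.5 reproduces only the d=0.56 figure. With n=10 and N=40, no tested pair of alpha and r reproduced all three within two points. With n=13 in the single condition and N=40, two quite different settings do: alpha .05 with three groups and r of about .415, and alpha .00625 with four groups and r of about .68. The alpha behind the figures cannot be recovered from them.

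**3. Dependence on r at .00625** (N=40, four groups).

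| r | time, d=0.48 | group by time, d=0.56 |
|---|---|---|
| .3 | 38% | 33% |
| .5 | 56% | 51% |
| .6 | 69% | 66% |
| .68 | 81% | 79% |
| .7 | 84% | 83% |

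At r=.5, about N=60 would be needed for 80% power at .00625 for either effect.

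**4. Holm against Bonferroni.** Holm compares the ordered p-values with .05/8 = .00625, .05/7 = .00714, .05/6 = .00833 and so on up to .05, stopping at the first failure. Any p-value at or below .00625 passes its own threshold, and so do all smaller ones; hence Holm rejects everything Bonferroni does. The gain comes only from later steps. For d=0.48 and r=.5, single-test power is 56% at the first threshold, 66% at the fifth (.0125) and 84% at the last (.05).

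Average power per truly changing ROI, from simulation of the time effect (d=0.48, N=40, r=.5, 40,000 trials per scenario, ROI correlation 0 to .7):

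| ROIs changing | Bonferroni | Holm | step-down max-T |
|---|---|---|---|
| 1 of 8 | 56% | 56% | 57-62% |
| 4 of 8 | 56% | 59-60% | 60-65% |
| 8 of 8 | 56% | 67-70% | 69-72% |

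No entry reaches 80%.

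**The case against.** The best defence is that the benchmark is explicitly non-binding in a pilot whose aim is to estimate effect sizes. No power is formally given up and no error rate is formally held, and choosing a valid, simple correction is not an error. That stands. It limits the point to an efficiency improvement, but .00625 is still the only named yardstick for the ROI tests, so it may as well be the better one.

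The defence also notes that the gain is small and depends on the scenario. Holm gains essentially nothing if one ROI changes. Its 11-14 points require all eight to change by the same amount, while the protocol itself says that different tactics engage different regions. Any extra gain from max-T depends on correlation among ROI change scores, for which the documents give no figure. All of this stands.

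Nor does the change settle multiplicity as a whole. The plan also tests connectivity, with 8·7/2 = 28 ROI pairs, and several ANOVA effects per ROI. A procedure over eight values covers none of that.

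A reader might infer that the stated detectable effects match 80% power only at an unadjusted .05, and so fail at .00625. The documents do not support this: alpha and r are both unstated, and at r near .68 both d=0.48 and d=0.56 reach about 80% at .00625. The reference to a single brain region hints at an unadjusted test but does not establish one.

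**Conclusion.** The point holds as a modest, free improvement together with a reporting gap. Holm controls the same 5% family-wise error as .00625 and never rejects fewer ROIs. At d=0.48, N=40 and an assumed r=.5, it adds 0, about 3-4 or about 11-14 percentage points of per-ROI power when one, four or eight ROIs change. The superiority of Holm needs no assumption; the size of the gain rests on r, on equal effects across the changing ROIs and on the number that change.

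Two stronger conclusions should not be drawn. The level is not a gate on publication, because the plan says it only helps with that judgement. And it is not shown that the sample misses its stated detectable effects at the corrected level, only that it does so unless r is about .68 or higher, a value the Power Analysis neither states nor justifies. Under r=.5 the step-down change recovers part of the lost power but does not restore 80%.

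**What to change.** In the Analysis Plan, replace the .00625 benchmark with Holm at family-wise 5% across the eight ROIs, applied separately to each ANOVA effect, and keep the sentence on its non-binding status. If permutation inference is preferred, a step-down max-T across the eight ROI values should be feasible with the permutation tool already named. Name one procedure in advance.

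In the Power Analysis, state the alpha, the between-session correlation and the number of groups, reconciling three with four. Report detectable effects at the corrected level for a range of r; at r=.5 these are about 0.60 for time and 0.71 for group by time. Detectable effects at .00625 remain the conservative statement under Holm, since its first step uses that level.

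The cost is a few sentences and, for max-T, minor computing. Holm loses nothing against Bonferroni in any scenario. The stated detectable effects will look less favourable unless a high r can be justified.

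### The post hoc correlation of symptom change with brain change states no group term, so a pooled version can turn significant through diagnosis alone when both changes differ by diagnosis

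*Combined protocol and SAP*

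**What the plan says.** The Approach section sets "N=40 adults (ages 18-50, approximately equal numbers of males and females" and defines the depressed group as "any participant who scores >1.5 SD from normative levels on the Beck-Depression Inventory-II". For the comparison group, "The non-clinical control group will have minimal symptoms on the BDI-II and State/Trait scales". It then says "Participants in each of these study groups then will be randomized into two conditions", with 10 per cell, so there are four cells: two diagnostic groups by two trainings.

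The Analysis Plan uses a "4 (ER group) × 2 (training timepoint) mixed-effects ANOVA" as the core test. On multiplicity it says "Because there will be 8 ROIs, we will consider results when using a Bonferroni-corrected α of .00625", and adds that the correction is not binding in a pilot.

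The Supplemental Analyses paragraph lists self-ratings, skin conductance, pupil and fixation measures, POMS-2, BDI-II and STAI. It closes by saying that change in these measures is typically "correlated with the degree of change in any brain regions found in the primary analysis", post hoc, as support for clinical relevance. No section gives a group term, a within-group or partial correlation, or a baseline covariate for this step.

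**The concern.** The grouping variable is built from one of the measures being correlated. Participants selected for a high BDI-II tend to score lower on repeat measurement, while controls near the floor have little room to fall. Mean BDI-II change is therefore likely to differ by diagnosis even if training does nothing. The same probably holds for STAI, on which controls are also selected to be low. No one is selected on POMS-2, self-ratings, skin conductance or pupil size, so the argument does not carry over directly to those.

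The 4 × 2 ANOVA can pick out a region because its change differs between groups. If that difference also runs along diagnosis, pooling all participants joins two separated clouds of points, and the gap between the clouds alone produces a correlation.

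This correlation is the step meant to link brain findings to clinical relevance, and the pilot is meant to inform larger grant proposals. A result driven by diagnosis would mislead that use.

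**Working it through.** **The plan's own figure.** 0.05 / 8 = 0.00625, which reproduces the stated Bonferroni level. No sample size, power or alpha is stated for the correlation itself.

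**Inputs from the documents.** 40 participants in four cells of 10, so 20 depressed and 20 controls; two change scores per person (brain, symptom); regions picked by the 4 × 2 ANOVA. With two timepoints, its group × time test is a one-way F(3, 36) on the change scores.

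**Assumed inputs.** The documents give no group differences in change, so a range is used, in within-group SDs of change: d₁ for brain and d₂ for symptoms, depressed versus control. The correlation within each group is set to zero. No dropout is assumed. Regions are picked at .05 unless stated, because the stricter level is not binding.

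**Expected pooled correlation.** With two equal groups and no within-group correlation,

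r = (d₁d₂/4) / √[(1 + d₁²/4)(1 + d₂²/4)].

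- d₁ = d₂ = 0.5: 0.0625 / 1.0625 = 0.06
- d₁ = 0.9, d₂ = 1.0: 0.225 / √(1.2025 × 1.25) = 0.18
- d₁ = 0.9, d₂ = 1.5: 0.3375 / √(1.2025 × 1.5625) = 0.25

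**False-positive rates by simulation** (four cells of 10, 40,000 to 200,000 replicates, two-sided .05). The pooled test has 40 − 2 = 38 df. The test adjusted for the four cells has 38 − 3 = 35 df.

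| Assumed truth | Pooled, no selection | Pooled, region picked by group × time at .05 | Adjusted for cell |
|---|---|---|---|
| Both differ by diagnosis, 0.5 SD | about 6% | about 9% | about 5% |
| Brain 0.9, symptoms 1.0, by diagnosis | about 21% | about 27% | about 5% |
| Brain 0.9, symptoms 1.5, by diagnosis | about 35% | about 47% | about 5% |
| No brain group difference, symptoms 1.0 by diagnosis | about 5% | about 10–11% | about 5% |
| Brain 1.0 by training arm only, symptoms 1.0 by diagnosis only | about 5% | about 5% | about 5% |

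In the fourth row the region was picked on a chance group difference. The pooled r averages zero, so the excess false positives fall in both directions.

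Picking regions at .00625 does not help. In the second and third rows the rate rises to about 34% and 58%, because the stricter rule keeps regions with larger observed group differences.

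**Regions picked by the time main effect.** With no group difference in brain change and a 1.0 SD symptom difference, the pooled rate is about 5%, so there is no material inflation. The condition matters: if brain change also differs by diagnosis, picking by time gives no protection. With both differences at 1.0 SD the pooled rate is about 24%, the same as with no selection.

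**The case against.** The strongest reply is that the text specifies no model. It describes what is typically done in such experiments, post hoc, in a hypothesis-generating pilot. A reader might infer that the plan prescribes an unadjusted correlation over all 40 participants. The documents do not say that; they leave the choice open. A reader might also infer that symptoms will be related to brain change only in ANOVA-positive regions. That restriction belongs to this one sentence. The same paragraph plans to relate brain change to many other factors, and the Clinical Assessment section puts the Table 3 scales, which include BDI-II and STAI, into exploratory sub-group analyses.

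Nor do the documents support the view that the correlation is inflated in general. The core hypothesis is that brain function will change, which is naturally a time effect, and the Power Analysis covers change common to all groups. A common change alone produces no inflation. The randomised contrast is training, and a brain difference by training alone produces none either. At 0.5 SD the unselected rate is close to nominal.

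It is also tempting to fault the restriction because it skips regions where people change in opposite directions. The remark that "individual brain function differences prior to ER training might be a potent determinant" concerns which neural changes follow training, not how they relate to symptoms, so testing every ROI is a preference.

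All of this limits the point. It does not remove it: a plain correlation run from this sentence would be the pooled one, and nothing in the plan rules that out or fixes the choice before results are seen.

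**Conclusion.** The point holds in a conditional form. A pooled correlation can be significant with no association inside any group if mean symptom change and mean brain change both differ by diagnosis. The first is likely for BDI-II and probable for STAI; the second is one of the outcomes the ANOVA can select. Under the assumed differences the false-positive rate runs from about 6% to 35% without selection and from about 9% to 47% after group × time selection at .05. A symptom difference alone, with selection on a chance brain difference, gives about 10–11%. These sizes rest on assumed group differences, zero within-group correlation and no dropout. Since the analysis is supplemental and the remedy needs no new data, this is a cheap improvement and not a flaw in the primary analysis.

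**What to change.** In the Supplemental Analyses paragraph, state that symptom change will be regressed on ROI change with the four cells and the baseline symptom score in the model, and that the within-cell partial correlation will be reported. Any pooled correlation should be shown as descriptive only.

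The cost is a few lines of analysis and four degrees of freedom: three for cell and one for baseline, so 38 falls to 34. The roughly 5% rate in the table is for adjustment by cell (35 df); the version with baseline was not simulated. Baseline BDI-II largely tracks diagnosis, so it will add limited information beyond cell.

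Reporting the same analysis for all 8 ROIs is optional and should be labelled exploratory. The .00625 level covers 8 tests. Three scales (POMS-2, BDI-II, STAI) across 8 ROIs make 3 × 8 = 24, so that level would not cover them.
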